Achieving a comfortable and functional connection between an amputee and their prosthetic limb is critical to the success of the prosthesis. Therefore, the socket system is the most significant component for overall success of the prosthesis^{1,2}. In an effort to maximize socket performance and comfort without adversely affecting residual limb health, a prosthetist custom fits a socket for every patient using plaster wraps or computer aided design. Currently, this process suffers from a lack of quantitative feedback to determine appropriate socket fit. Prosthetists aim to minimize suspension-dependent movement between the socket and residual limb, but current approaches are limited as they rely on anecdotal visual cues along with subjective verbal feedback from the patient. Prosthetists then use this information to revise socket parameters such as volume, geometry, and type of suspension to provide current 'best' fit for a patient. Regardless of prosthetist fitting, the volume of mature residual limb (>18 months post-amputation³) are subject to daily⁴ and chronic^{5,6} changes in volume that compromise socket fit and performance. For the 1 million Americans that live with a lower-limb amputation, a growing number of which are service men and women⁷⁻⁹, these volume changes adversely affect fit, performance, and residual limb health⁶ – including skin breakdown and ulceration¹⁰ that can necessitate revision of the amputation. Indeed, for traumatic lower-limb amputations, the requirement for surgical revision is known to be as high as 30%¹¹.

II. Objective:

Aim 1 will evaluate the relationship between vacuum pressure and limb movement inside the socket and how it changes with respect to vacuum pressure setting, gait speed and socket volume

Aim 2 will evaluate the impact of socket movement on residual limb circulation and residual limb skin health

Aim 3 will compare the effectiveness of an adaptive vacuum system to standard of care suspension prosthetics (pin-locking or suction).

Study Population: Up to 170 amputees will be enrolled in the study overall.

1. **Aim 1:** 10 trans-femoral amputees and 10 trans-tibial amputees will be enrolled.
2. **Aim 2:** 15 trans-tibial and 15 trans-femoral amputees will be enrolled.
3. **Aim 3:** n=120 (trans-tibial and trans-femoral amputees) will be enrolled.

III. Inclusion Criteria:

1. Ages of 18 and above

2. Unilateral trans-tibial or trans-femoral amputee
3. Ambulate at a K2 level or higher
4. At least 3 months post-amputation per physician discretion
5. Residual limb length greater than 6.5 inches in length
6. Able to follow directions and give informed consent on their own or through Legally Authorized Representative.
7. Must be able to ambulate without assistance. An external assistance device such as cane or walker will be permitted.
8. Adequate arterial blood flow of the index stump as evidenced by TcOM > 30 mmHG, measured within the past 12 months.

IV. Exclusion Criteria:

1. Conditions that prevent wearing a prosthetic socket; such as existing scab, ulcer, or keloid scar on amputation stump.
2. Cognitive deficits or mental health problems that would limit ability to consent and participate fully in the study protocol
3. Women who are pregnant or who plan to become pregnant in the near future

V. Study Design:

This study has 3 aims where trans-femoral and trans-tibial amputees will be enrolled.

Subjects enrolled in Aim 1 (N=20) will have one study visit that will take place at The Ohio Willow Wood (OWW).

Subjects enrolled in Aim 2 (N=30) will have a total of 4 visits at baseline, month 1, month 2, and month 3.

Subjects in Aim 3 (120) will be enrolled at Indiana University (n=30 subjects), OWW (n=30), and at Walter Reed National Military Medical Center (WRNMMC) (n=60 subjects) with a total of 3 visits at 0 week (baseline), 0-4 weeks (socket fitting visits), and 16 weeks (final visit).. OWW and Walter Reed National Military Medical Center (WRNMMC) have separate IRB protocol & approval to conduct their part of subject recruitment and study visits. Aims 2 and 3 will not be run concurrently. Subjects enrolled in Aim 2 can participate in Aim 3. Aim 2 studies performed at Ohio State and Indiana University. Aim 2 has enrolled 15 subjects through Ohio State University & OWW (and these 20 subjects have completed their participation in the study) and the data is currently being analyzed to determine if additional subjects are required. If analysis shows sufficient subjects have been enrolled to achieve the study aim, no additional subjects will be enrolled in Aim 2. If there is insufficient data, the remainder of the Aim 2 subjects will be enrolled through OWW under their approved IRB with WIRB. Aim 3 studies performed at IU, OWW and WRNMMC per their approved IRB protocols. The vacuum suspension used for the study is new to all enrolled subjects

We are requesting the use of ResearchMatch.org for subject recruitment on this protocol. See attached General Description of ResearchMatch attached.

Descriptions of prosthesis suspension platforms:

Pin-locking prosthesis: A gel-liner with an attached pin, lanyard, KISS system that clicks into a locking mechanism (receiver) inside the socket.

Suction prosthesis: A total contact weight bearing socket with a one-way expulsion valve to let air out.

Adaptive vacuum test prosthesis (“test” system): The adaptive vacuum prosthesis is sold as a commercial device by the company Willow Wood with suggested U.S. L-Code L5781. The device is designated as a Class 1 Medical Device and 510(K) Exempt. This category is part of a low or moderate risk to patient safety and health. The Prosthetic socket system uses an active vacuum pump to push air out of the socket. The level of vacuum is controlled by hardware that automatically detects the socket fit based on in-socket motion and adjusts vacuum as needed to eliminate this motion.

VI. Aim 1 (Completed):

1. **Study Visit 1** This initial visit will take place at The Ohio Willow Wood and the following research activities will take place:
 - Informed Consent will be obtained
 - Baseline demographics, medical history, and medications will be recorded
 - Verify fit of the thermoplastic socket
 - Subject will perform multiple ambulation trials at controlled cadences while the vacuum pump is set turned off (0 inHg), 7 inHg, 10 inHg, 13 inHg, and 20 inHg.
 - Subject will repeat the ambulation task with different thickness liners to simulate global volume changes.
 - Subject will repeat the ambulation task with a gel pad insert to simulate local volume changes.

VII. Aim 2 (partially completed if additional subjects are needed, they will be recruited at OWW with their approved IRB protocol):

1. **Study Visit 1 (Baseline)** This initial visit will take place at OSUWMC & OWW where the following research activities will take place:
 - Informed Consent will be obtained

- Baseline demographics, medical history, and medications will be recorded
- Subjects will perform seated tasks, standing tasks, and walking on a treadmill task. Skin health measurements will be taken before and after the activity period.
- Hyperspectral Imaging – A non-invasive visible light imaging technology will measure tissue oxygenation
- Hitachi Aloka Ultrasound – A hand held device will be moved gently across the skin and measure your blood flow of deeper skin tissues.
- Skin Temperature-A small tab (small sticker) will be placed on the skin and tell us the temperature of your residual limb
- Surface Electrical Capacitance – Small non-invasive probe place on skin to measure skin hydration
- Trans epidermal water loss measurement (TEWL) – Small non-invasive probe compares relative humidity of skin surface to indicate epidermal barrier function
- Transcutaneous Oxygen Measurement – Small non-invasive probe measures the amount of oxygen released through the skin layer
- This data will be used to determine how socket movement affects the limb health measurements
- The study prosthetist will set vacuum level set to first level
- Digital Image

2. Study Visit 2, 3, 4 (month 1, 2, 3) Subjects will return at 1, 2, and 3 months after study visit 1 where the following research activities will take place:

- Subject will perform seated tasks, standing tasks, and walking on a treadmill task. Skin health measurements will be taken before and after the activity period.
- Hyperspectral Imaging
- Hitachi Aloka Ultrasound
- Skin Temperature
- Surface Electrical Capacitance
- TEWL measurement
- Transcutaneous Oxygen Measurement
- This data will be used to determine how socket movement affects the limb health measurements
- The study prosthetist will set the vacuum level set to the next treatment level except at study visit 4.
- At the end of visit 4, patients will be returned to their standard of care prosthesis. The study prosthetist will be available to review and adjust the fit of their existing prosthesis.
- Digital Image

VIII. Aim 3 (n=30 will be performed at IU under current approved protocol):

Rationale for the amendment: As per the approved DoD proposal, n=60 (n=30 each at IU and Willow wood for Limb Heath analysis, current approved IU IRB protocol) and n=60 subjects were supposed to be completed at Walter Reed (WR) for Functional analysis. We have received a request from WR to perform Functional analysis on the remaining subject that will be enrolled for limb health analysis (this is due to COVID-19 and availability of subjects at WR. The request from WR was also in view of short time line remaining (study end date 09/2021).

After receiving consent, the first enrollment visit will be scheduled for the subjects to see the IU study prosthetist to initiate the “test” socket fitting visits.

On this day, prior to socket fitting activities, the arterial blood flow will be measured on the index stump if not already completed per standard of care within the previous 12 months prior to enrollment for data analysis. Those with an TcOM < 30 mmHG be excluded and no further study activities will be completed. These subjects will be recorded as a screen fail and will not be enrolled.

Others will move forward with socket fitting activities.

- A. **Study Visit #1 - Socket Fitting visits (Week 0 - 4, +/- 2 weeks) – Note: this visit may consist of three (minimum) visits plus socket adjustment visits (as needed by the subject) on separate days (up to 4 weeks)**
 - i) limb shape capture, measurements or tracing
 - ii) diagnostic static fitting and diagnostic dynamic fitting
 - iii) delivery of definitive “research” socket

Once delivery of the definitive research socket has been completed, the subject will be allowed to return for no greater than 4 adjustments (within 0-2 weeks from baseline) to obtain a comfortable fit in order to complete this study. If subject requires more than 4 adjustment visits, the participation from the study will end.

Once the subject is comfortable with the fitting, the date will be noted by the study team as **“research socket use start date”**. From this date, the subject will begin wearing the test socket for next 16 weeks.

- B. **Study Visit #2A - Baseline visit for residual limb health (Week 4, +/- 2 weeks)** Enrollment, after delivery of the definitive research socket and completion of the socket fitting visits, the following research activities will take place to obtain baseline measurements:

- Subjects will be asked to walk on a treadmill for 10 mins. The residual and sound (intact) limb health measurements will be taken before and after the activity period with the exception of conducting post-activity ultrasound and digital imaging. The purpose of acquiring ultrasound and digital imaging is to determine changes in skin structure on a long-term basis; thus, these measurements will only be collected during pre-activity procedures to observe changes in a resting state. The following health measurements will take place:
 - Surface Electrical Capacitance
 - TEWL measurement
 - Hyperspectral Imaging
 - Ultrasound (pre-activity only)
 - Perfusion/ Blood flow
 - Digital Image (pre-activity only)

B.i. Study Visit #2B - Baseline visit for gait assessment (Week 4, +/- 2 weeks)**

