***Note* Study Visit #2A and #2B can be combined and performed in a single study visit upon the discretion of the subject.**

Subjects will begin in their current standard of care prosthesis (the prosthesis worn at time of study enrollment), wherein the following research activities will take place in the following order:

- Subjective questionnaires [Veterans RAND 36-Item Health Survey (VR
- 36, PEQ, Socket Comfort Scores (SCS), and National Institute of Health (NIH) Patient-Reported
- Outcomes Measurement Information System (PROMIS)
- Functional evaluation [Comprehensive High-level Activity Mobility Predictor (CHAMP)]
- Biomechanical evaluation of gait during 6min walking test
 - a. Positioning markers will be placed on the subject while performing the walking assessment to track and describe the movement of the body in three dimensions.
- Repeat SCS outcome

**** applicable to any new enrollments and/or any already enrolled subject completed their limb health part (16 weeks in test sockets followed by 4 weeks in SoC socket as wash off period)**

Following completion of these activities in study visit 2A & B, the subjects will be fitted with the adaptive vacuum suspension by a certified prosthetist that they will wear subsequently wear the device for 16 weeks

The study team will follow up subjects with a weekly phone call to determine the compliance for the use of research socket.

C. **Study Visit #3A – Final Visit (Week 16, +/-2 weeks).** After 16 weeks of wearing the “research” socket the following research activities will take place in the following order:

- Subjects will be asked to walk on a treadmill for 10 mins. The following residual and sound limb health measurements will be taken before and after the activity period with the exception of conducting post-activity ultrasound and digital imaging, is as follows
 - Surface Electrical Capacitance
 - TEWL measurement
 - Hyperspectral Imaging
 - Ultrasound (pre-activity only)
 - Perfusion/ Blood flow
 - Digital Image (pre-activity only)

C.i **Study Visit #3B**— the visit will take place either the same day of Visit 3A or another day within the Week 16, +/-2 weeks based on subject convenience, to repeat research activities previously performed in study visit # 2A

- Subjective questionnaires [Veterans RAND 36-Item Health Survey (VR 36, PEQ, Socket Comfort Scores (SCS), and National Institute of Health (NIH) Patient-Reported Outcomes Measurement Information System (PROMIS)]

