- Functional evaluation [Comprehensive High-level Activity Mobility Predictor (CHAMP)]
- Biomechanical evaluation of gait during 6min walking test
- Repeat SCS outcome

- The subjects will be given a choice to keep the research socket or return to using their original prosthesis as normal. The study prosthetist will be available to review and adjust the fit of their standard of care prosthesis at this time. Note; Due to physical change and limb volume fluctuation over the study period, it is possible that at the end of the study the standard of care prosthesis will not fit your residual limb as it does at the beginning of the study. At the completion of the study it is recommended that the subject follow up with their primary care prosthetist for socket evaluation and fitting.
- Any research-related tests or activities are performed at the expense of the research study and will not be billed to you or your insurance.
- Any non-research related activities, tests, or necessary medical treatment will be provided to you and billed as part of your medical expenses. Costs not covered by your health care insurer will be your responsibility. Also, it is your responsibility to determine the extent of your health care coverage.

Walter Reed National Military Medical Center (WRNMMC) will recruit and enroll 60 subjects with a pin-locking prosthesis and has separate IRB approval to conduct the study. The study visits will be per their approved IRB protocol (see attached).

IX. Study Procedures:

There may be risks that are not known about at this time. Side effects, risks, and discomforts may result from study participation.

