All subjects will be compensated \$100 for each of the completed visits. Aim 1 subjects will be compensated \$100 for the completed study visit 1. Aim 2 subjects will have 4 total visits and will be eligible for a maximum of \$400 for completion of all study visits. Aim 3 subjects will have 3 total visits and will be eligible for a maximum of \$450 for the completion of all visits per following schedule: Visit #1 (\$50), Visit #2A & B (\$150, for completing all socket fitting activities

& baseline) and Visit #3A&B (\$250). Subjects will not be paid if any of study visits are not completed.

XV. Statistical Analysis:

Patient demographics and clinical characteristics will be described using frequencies and percentages for categorical data and median and the interquartile range (IQR) for continuous data. In Aim 1, random-effects linear regression will be used to assess the relationship between wave amplitude and distal movement (or lateral shift) controlling for vacuum pressure. Patient ID will be the random-term in the model. In Aim 2, random-effects linear regression will also be used to compare percent change in limb perfusion across adaptive EVS and suction at 12 weeks controlling vacuum pressure and controlling for the baseline EVS and suction values. In Aim 3, a random-effects linear regression model will be used to establish the relationship in amputee performance (as measured by the CHAMP tasks) and residual limb health across EVS and suction and across EVS and pin-locking/lanyard in a cross-over design. The model includes terms for group (EVS vs. suction or EVS vs. pin-locking/lanyard), sequence (EVS to suction vs. suction to EVS or EVS to pin-locking/lanyard vs. pin-locking/lanyard to EVS), and visit (second vs. first). All statistical models will account for the effect of age, diabetes status and smoking history by including them as the covariates in the models. As per need, subjects may be stratified based upon diabetes status and arterial blood flow status. The *p*-values produced in the study will be adjusted using the Holms procedure to control the overall type I error at 0.05 due to the multiple comparisons. All analyses will be run using Stata 13.1, Stata Corporation, College Station, Texas.

XVI. References:

1. Lake, C. The evolution of upper limb prosthetic socket design. *Journal of Prosthetics and Orthotics* 20, 85 (2008).

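### Aim 3 as scheduled runs in one order and admits limbs from 3 months post-amputation, so natural change in recent amputees may be read as device effect; add a pre-specified estimate in limbs over 18 months

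*Combined protocol and SAP*

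**What the plan says.** **Entry.** Inclusion criterion 4 (Section III) reads "At least 3 months post-amputation per physician discretion". There is no upper limit, and no stratum by time since amputation.

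**Maturity.** The background paragraph before Section II speaks of the "mature residual limb (>18 months post-amputation") and says that even these limbs undergo daily and chronic volume change.

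**Aim 3 schedule (Section VIII).** The functional baseline is headed "Baseline visit for gait assessment (Week 4, +/- 2 weeks"), and its first instruction is "Subjects will begin in their current standard of care prosthesis (the prosthesis worn at time of study enrollment"). The limb-health baseline comes "after delivery of the definitive research socket and completion of the socket fitting visits". Both sets of outcomes are repeated at week 16, give or take 2 weeks, after wear of the research socket. Subjects who had already finished the limb-health part spend 4 weeks back in their standard socket, and then also go from standard to test for the gait comparison. Section VIII describes no reversed order, no concurrent control and no outcome visit after a return to the standard prosthesis. Its closing notes warn that the old prosthesis may no longer fit, "Due to physical change and limb volume fluctuation over the study period".

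**Aim 3 analysis (Section XV).** The model is a random-effects regression in a cross-over design, with group, sequence (both orders) and visit terms. The covariates are "age, diabetes status and smoking history". Optional stratification is by diabetes and arterial flow.

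**The concern.** In a one-order, within-subject comparison, whatever changes between baseline and final visit is attributed to the device. A limb that the protocol would not yet call mature is a plausible source of such change, in either direction. Recovery could flatter the vacuum system, and unfavourable change could count against it.

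The listed covariates do not address this. Time since amputation is not among them. Subject-level main effects such as age or smoking also shift both visits of a subject equally, so they cannot remove drift from a within-subject contrast.

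**Working it through.** The plan states no power, effect size, SD or dropout for Aim 3, so there is no figure of its own to reproduce beyond the enrolment sum (30 + 30 + 60 = 120).

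**1. Can the stated model separate device from time?** Take the fixed effects of Section XV: intercept, group, sequence and visit.
- One order, standard then test, for all subjects: the group and visit columns are identical (correlation 1.0) and the sequence column is constant. The matrix has rank 2 of 4, so device and time are aliased and the sequence effect cannot be estimated.
- Two balanced orders (15 and 15): rank 4 of 4, and the group-visit correlation is 0.

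**2. Where does a recent amputee fall?** Take a new subject entering at 3 months, with 4.345 weeks per month.
- Baseline at week 2 to 6: 3 + 2/4.345 = 3.5 months to 3 + 6/4.345 = 4.4 months.
- Final visit, earliest (week 14 from enrolment): 3 + 14/4.345 = 6.2 months.
- Final visit, latest (18 weeks of wear from week 6, so week 24): 3 + 24/4.345 = 8.5 months.

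Both measurements lie well before 18 months. The gap between them is 8 to 16 weeks if visit weeks count from enrolment (14 − 6 and 18 − 2), or 14 to 18 weeks if they count from the start of wear.

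**3. How large could the bias be?** All inputs here are assumptions: a share *f* of subjects at 18 months or less, a natural drift *d* in those subjects in SDs of the change score, no drift in the others, and no true device effect.

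Bias = *f* × *d*. SD of the change = √(1 + *f*(1 − *f*)*d*²). SE = SD/√n. Rejection rate = 1 − Φ(1.96 − bias/SE) + Φ(−1.96 − bias/SE).

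Worked case, *f* = 0.5, *d* = 0.5, n = 60: bias = 0.25; SD = √1.0625 = 1.031; SE = 1.031/7.746 = 0.133; bias/SE = 1.88; rejection rate = 46.8%.

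| Share × drift | Bias (SD) | n=30 | n=60 | n=120 |
|---|---|---|---|---|
| 10% × 0.2 | 0.02 | 5.1% | 5.3% | 5.5% |
| 25% × 0.2 | 0.05 | 5.9% | 6.7% | 8.5% |
| 25% × 0.5 | 0.125 | 10.3% | 15.7% | 26.8% |
| 50% × 0.5 | 0.25 | 26.4% | 46.8% | 75.7% |

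A noncentral-t calculation that ignores the mixture variance gives 47.8% for the last case at n=60, hence the range of about 5% to 48%. Here n=30 is the Indiana cohort, n=60 is Indiana plus Ohio Willow Wood, and n=120 is all of Aim 3. The rates are for one comparison at an unadjusted two-sided 0.05; Holm adjustment would lower the rate for each comparison.

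**4. What would two orders do?** In a simulation at 25% × 0.5 SD, one order gives a mean bias of about 0.12 SD at n=30 and 0.13 SD at n=60. Two balanced orders give about 0.00. The false-positive rate falls from 9.5% to 4.7% at n=30, and from 15.2% to 4.6% at n=60.

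**The case against.** **Section XV specifies a cross-over.** This is the strongest objection. If both orders were run, the visit term would absorb the average drift, as step 4 of the working shows. It stands as a condition: the protection is real only if the reversed order exists, and Section VIII does not describe one. The conflict between the two sections is the more basic defect, and time since amputation is one source of drift that it lets through.

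**Maturity is mentioned only in connection with limb volume.** Volume is not a listed Aim 3 outcome, and nowhere do the documents say that skin measures or CHAMP drift between 3 and 18 months. The warning about fit is addressed to all subjects. This stands, and it is why the point says that change may be misread, not that it will be.

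**The share of recent amputees may be small.** K2 ambulation or better, an intact stump, adequate TcOM, physician discretion and an existing prosthesis for the gait baseline all select against very recent amputees. At 10% × 0.2 SD the error rate is practically nominal. This also stands. Physician discretion, however, is a clinical safeguard and does not control confounding.

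**The sound limb could serve as a control.** It is measured for the limb-health outcomes only, is not in the stated model, and offers nothing for CHAMP or the questionnaires.

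**A reader might infer that a visit by time-since-amputation term would correct the bias.** It would not. With one order, visit and device are the same column, so the term cannot tell natural recovery from a device that works differently in recent amputees.

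**A reader might also infer that limbs over 18 months are free of drift.** The background paragraph says that they change too.

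**Conclusion.** The point holds within limits. As Section VIII is written, device and time are aliased in Aim 3. Entry from 3 months admits limbs that the protocol does not call mature, and nothing in the stated analysis deals with time since amputation.

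It would be tempting to conclude that natural limb change is in fact being counted as device benefit. The documents do not support that: they give no share of recent amputees, no drift and no SD, and the direction is open. The bias of 0.02-0.25 SD rests wholly on the assumed shares and drifts, and at the low end it is negligible.

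The conclusion covers the schedule supplied here. Ohio Willow Wood and Walter Reed work under separate IRB protocols. The Walter Reed visits (60 of the 120 subjects) follow a protocol not supplied, so the order of measurement there cannot be checked. No view is taken on the clinical entry limit.

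**What to change.** 1. Reconcile Sections VIII and XV. Either describe how the second order is obtained, or state that Aim 3 is a one-order comparison and drop the model terms that it cannot estimate.
2. Leave eligibility and visits unchanged. Derive time since amputation at enrolment from the information used to check criterion 4.
3. Pre-specify as a sensitivity analysis the Aim 3 device estimate in limbs more than 18 months post-amputation, reported beside the all-subjects estimate. State that it reduces time confounding but does not remove it, because mature limbs also change.
4. A visit (here equal to device) by time-since-amputation term may be reported as exploratory heterogeneity only, with the statement that it cannot separate natural recovery from a device effect that differs in recent amputees.

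**Cost.** No new visits, and one derived variable. If only a yes or no was recorded for criterion 4, one date per subject has to be recovered. The sensitivity interval is wider by 1/√(1 − share excluded), other things equal: 1/√0.7 = 1.20, about 20% wider if 30% are excluded, and 1/√0.5 = 1.41, about 41% wider if 50% are.

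### Aim 2's EVS-versus-suction model adjusts for vacuum pressure, which is part of the device contrast, and its adaptive label is not supported by a visit schedule of prosthetist-set levels

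*Combined protocol and SAP*

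**What the plan says.** Four places in the combined protocol and SAP bear on what Aim 2 subjects received and how it is analysed.

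- **Section VII, Visit 1:** "The study prosthetist will set vacuum level set to first level".
- **Section VII, Visits 2 to 4:** "The study prosthetist will set the vacuum level set to the next treatment level except at study visit 4".
- **Section V, descriptions of suspension platforms,** on the adaptive test prosthesis: "The level of vacuum is controlled by hardware that automatically detects the socket fit based on in-socket motion and adjusts vacuum as needed". The stated purpose is to remove the motion.
- **Section XV:** the Aim 2 model is to "compare percent change in limb perfusion across adaptive EVS and suction at 12 weeks controlling vacuum pressure", with adjustment for baseline values as well.

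Section II gives the objective in other terms: "Aim 2 will evaluate the impact of socket movement on residual limb circulation and residual limb skin health". It leaves the comparison of the adaptive system with standard suspension to Aim 3.

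The documents do not define the Aim 2 levels or their order. They do not say whether automatic control was on, off or limited by the set level. Nor do they say whether vacuum pressure in Section XV means the set or the delivered value. The Aim 2 visit lists include neither a recording of delivered vacuum nor a suction period.

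**The concern.** Two things follow from reading these sections together.

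First, the condition that Section XV names is not the one that Section VII visibly assigns. Section VII assigns levels chosen by the prosthetist, whereas Section XV reports on a system that chooses its own. A perfusion result could therefore be credited to a control mode that subjects did not wear.

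Second, vacuum pressure is a large part of what distinguishes EVS from suction. Section V describes EVS as using an active pump and suction as using a one-way valve. Adjusting the device comparison for pressure asks what the device does with its pressure held equal to that of suction. That is not the effect of wearing one system rather than the other, and in a plausible case it cannot be estimated. Section V says that Aim 2 data are being analysed to decide whether more subjects are needed, so the label and the model term matter now.

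**Working it through.** The plan gives no power calculation or other figure to reproduce here. The check is a comparison of the sections, followed by a short calculation on the model term.

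**Step 1. What was assigned.** Levels are set at Visits 1, 2 and 3 and not at Visit 4. That makes three settings, each worn for about a month. The month 3 measurement, taken here as the 12-week analysis point, follows the third setting.

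**Step 2. What vacuum pressure could mean in Section XV.**

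- *Delivered pressure, automatic control active.* The device raises or lowers vacuum in response to in-socket motion. Delivered pressure is then a consequence of the device and of the movement that Aim 2 studies. Conditioning on it removes part of the device effect.
- *Set pressure.* The prosthetist assigns it, so it does not respond to motion. It is still tied to device, because only EVS subjects have a set level.

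**Step 3. Size of the problem for set pressure.** Write the model as E(Y) = a + bD + cP, with D = 1 for EVS and 0 for suction. Let suction have a common pressure p0. Let the EVS levels have mean m and variance s² (divisor equal to the number of levels), with equal group sizes. Then:

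- unadjusted EVS-minus-suction difference = b + c(m − p0), so b alone is not the difference between the conditions as worn
- R² between D and P = (m − p0)² / [(m − p0)² + 2s²]
- VIF for D = 1/(1 − R²) = 1 + (m − p0)²/(2s²)

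Assumptions, none stated for Aim 2: p0 = 0 inHg, balanced groups, and levels borrowed from Aim 1, where subjects walked "while the vacuum pump is set turned off (0 inHg), 7 inHg, 10 inHg, 13 inHg, and 20 inHg".

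| EVS levels at the analysis visit (inHg) | m | s² | VIF | SE multiplier, √VIF |
|---|---|---|---|---|
| 7, 10, 13, 20 | 12.5 | 23.25 | 1 + 156.25/46.5 = 4.4 | 2.1 |
| 7, 10, 13 | 10 | 6 | 1 + 100/12 = 9.3 | 3.1 |
| 10, 13, 20 | 14.33 | 17.56 | 1 + 205.44/35.11 = 6.9 | 2.6 |
| 7, 13, 20 | 13.33 | 28.22 | 1 + 177.78/56.44 = 4.1 | 2.0 |
| all subjects on one common level | that level | 0 | infinite (R² = 1) | not estimable |

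The last row applies at month 3 if every subject steps through the levels in the same order. Perfect collinearity then holds for any common suction pressure that differs from the EVS level. In the other rows the VIF falls as p0 approaches m. If all monthly visits entered the model, the spread rows would be the closer guide, and only roughly, because the patient random effect changes the weighting.

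**The case against.** The strongest reply is that nothing here is shown to be contradictory. Section VII never says that the level is fixed. A set-point, or a starting level with automatic adjustment around it, fits both Section VII and Section V. Aim 1 shows that set levels are an established way of running the pump in this programme, and Section II leaves the adaptive comparison to Aim 3. On that view the defect is one misplaced word in Section XV. Any further Aim 2 enrolment also runs under the Ohio Willow Wood site's own approved protocol, which may define levels and mode.

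Much of this stands. A reader might infer that the two descriptions cannot both be true of one device, or that Aim 2 can say nothing about adaptive EVS. The documents do not support either inference, because they do not say what a level is. A reader might also take Aim 1's range of 0 to 20 inHg as the possible gap between set and received vacuum. That range belongs to another aim and bounds nothing in Aim 2.

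A second reply is that vacuum may confound the relation between movement and perfusion, so removing it could introduce bias. That is a fair point for the socket-movement objective. It is why the change below is confined to the device comparison, with level handled in its own model.

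The covariate problem is not answered by either reply. It is present whether pressure is set or delivered, and a definition held in another protocol would not remove it.

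**Conclusion.** The point holds in a limited form. Sections V, VII and XV must be reconciled, because the Aim 2 visit schedule does not support the adaptive EVS label as it stands. The documents do not show which control mode was used.

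The firmer finding is that vacuum pressure should not be an adjustment covariate in the EVS-versus-suction perfusion comparison. If it is delivered pressure, it lies on the path by which the device acts. If it is set pressure, it is near or perfectly collinear with device: VIF of 4.1 to 9.3 with levels spread across subjects, infinite with one common level at month 3. These figures rest on suction at 0 inHg, balanced groups and Aim 1's levels. They illustrate the problem and are not estimates for Aim 2.

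The issue applies to the whole Aim 2 device comparison (planned n = 30, partly completed). It is separate from the absence of a suction period in the Aim 2 visits, which leaves the comparison without a visible comparator however EVS is labelled.

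**What to change.** 1. In Section XV, remove vacuum pressure from the Aim 2 EVS-versus-suction model.
2. If levels were held, analyse assigned level as the exposure in a separate within-EVS model for the socket-movement objective. State the order in which levels were given: with one common order, level and month cannot be separated in that model, and the result should be reported as descriptive.
3. If automatic control was active, do not treat the set level as the exposure. Report delivered pressure as a description where it was recorded.
4. In Section VII, state the control mode actually used and what a treatment level means, and reconcile this with Sections V and XV. Name the Aim 2 condition by that mode and limit the conclusion to it. For subjects already treated, this means reporting what was done.

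The cost is wording in Sections VII and XV, one model term dropped and one secondary model added, with no new visits or subjects. The downside is that, if levels were held, Aim 2 cannot be presented as evidence on the adaptive system. The change does not repair the missing suction period. No vacuum level or control mode is recommended here; that choice is the sponsor's.
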